#### **6.2.12.4 Lambda-z ( $\lambda_z$ ) Acceptance and AUCinf Reporting Criteria**

The following criteria will be used to report lambda-z and related parameters:

- At least 3 quantifiable concentration-time points should be used in the regression
- Cmax or data prior to Cmax should not be included in the regression
- Adjusted R^2 should be  $\geq 0.8000$

If these acceptance criteria are not met, lambda-z and descriptive parameters such as the time range for the regression, adjusted R^2, etc. will be retained in a parameter listing for informational purposes. Lambda-z will be excluded from summary statistics and from subsequent PK calculations; parameters calculated using lambda-z (e.g. t1/2, AUCinf, CL/F, and Vz/F) will be reported as ND (not determinable).

If lambda-z acceptance criteria are met and AUCinf is estimable, the following criteria are used to report AUCinf:

- The percentage of AUCinf based on extrapolation should be  $<20.0\%$ .

If the percentage of AUCinf based on extrapolation is 20.0% or greater, AUCinf and AUCExtrap will be retained in a PK parameter listing for informational purposes; these parameters will be excluded from summary statistics, subsequent PK calculations (e.g., CL/F, Vz/F), and statistical analysis (e.g. ANOVA).

### **6.3 Conventions**

All clinical data summaries, statistical analyses and listings will be generated using SAS (Version 9.4 or higher). Data summaries and analyses will be reported within Appendix 14 and individual data listings within Appendix 16.2 of the CSR.

Subject disposition, baseline characteristics, demography and adverse event data will be presented by treatment group and overall. Other safety data will be presented by treatment group only or overall.

QMD Ref: Worldwide-TMP-ST-006-4.0 Effective: 12Aug2019	Governing QMD: Worldwide-SOP-ST-001
Confidentiality Statement	

This document is the property of Worldwide Clinical Trials Inc. and may not be duplicated, copied, altered or removed from company without prior approval from Worldwide Quality Assurance or in compliance with Worldwide Standard Operating Procedures.

Worldwide Clinical Trials Controlled Quality Management Document								
WORLDWIDE CLINICAL TRIALS			Sponsor:	Global Alliance for TB Drug Development				
			Protocol Number:	TBAJ-876-CL001				
STATISTICAL ANALYSIS PLAN – PHASE 1								

Treatment group labels will be displayed as follows:

### Part 1 SAD - TBAJ-876 Oral Suspension

Placebo	TBAJ-876 (10 mg)	TBAJ-876 (25 mg)	TBAJ-876 (50 mg)	TBAJ-876 (100 mg) Fasted	TBAJ-876 (100 mg) Fed	TBAJ-876 (200 mg)	TBAJ-876 (400 mg)	TBAJ-876 (800 mg)
---------	---------------------	---------------------	---------------------	--------------------------------	-----------------------------	----------------------	----------------------	----------------------

### Part 2 MAD - TBAJ-876 Oral Suspension

Placebo	TBAJ-876 (25 mg)	TBAJ-876 (75 mg)	TBAJ-876 (TBD mg)
---------	---------------------	---------------------	----------------------

### Part 3 BA - TBAJ-876 Tablets

TBAJ-876 (1x100 mg) Fasted	TBAJ-876 (1x100 mg) Fed	TBAJ-876 (4x25 mg) Fasted
----------------------------------	-------------------------------	---------------------------------

Continuous variables will be summarized by the number of non-missing observations, mean, median, standard deviation, and minimum and maximum.

Categorical variables will be summarized by presenting the frequency and percent. Percentages will be based on the number of non-missing observations or the subject population unless otherwise specified. For each variable, all categories will be shown. Zero frequencies (but not the percent) within a category will be presented.

Listings will be sorted in the following order, treatment group, subject, parameter, and visit unless otherwise stated. All data will be listed, subjects who were not randomized will be displayed after the randomized treatment groups.

PK data listings, summaries, figures, and statistical analyses will be generated using Phoenix™ WinNonlin® (Version 8.3.4 or higher) or SAS (Version 9.4 or higher). PK concentration data will be summarized by study part, analyte, and cohort (or group for Part 3), and study day for Part 2 at each nominal sample time. PK parameter data will be summarized by study part, analyte, and cohort (or group for Part 3), and study day for Part 2. PK data will also be stratified by gender within each cohort.

QMD Ref: Worldwide-TMP-ST-006-4.0 Effective: 12Aug2019	Governing QMD: Worldwide-SOP-ST-001
Confidentiality Statement	

This document is the property of Worldwide Clinical Trials Inc. and may not be duplicated, copied, altered or removed from company without prior approval from Worldwide Quality Assurance or in compliance with Worldwide Standard Operating Procedures.

Worldwide Clinical Trials Controlled Quality Management Document		
 WORLDWIDE CLINICAL TRIALS	Sponsor:	Global Alliance for TB Drug Development
	Protocol Number:	TBAJ-876-CL001
STATISTICAL ANALYSIS PLAN – PHASE 1		

PK concentration-time data will be summarized by the number of non-missing observations (n), arithmetic mean (mean), standard deviation (SD), median, minimum (min), maximum (max), coefficient of variation (CV%), and geometric mean. PK parameter data will be summarized by n, mean, SD, median, min, max, CV%, geometric mean, and geometric CV%. Summary statistics that are not calculable due to lack of quantifiable data will be presented as NC in the descriptive statistic tables.

### 6.3.1 Decimal Places

For summary statistics, n will be reported as a whole number. Means, medians and percentiles will be displayed to one more decimal place than the data, dispersion statistics (e.g. standard deviation) will have two more decimal places, and the minimum and maximum will be displayed to the same number of decimal places as reported in the raw data. Percentages will be displayed with one decimal place. All data presented in the individual subject listings will be as recorded on the eCRF.

For PK data, individual concentrations and individual PK parameters will be reported 3 significant figures. For summary statistics, n will be reported as a whole number; mean, standard deviation, median, minimum, maximum, CV%, geometric mean, and geometric CV% will be reported to the same precision as for individual data.

## 6.4 Subject Disposition

Subject disposition will be summarized as follows:

- The number of subjects who were enrolled, who were randomized and who are in each analysis set will be summarized by treatment group and overall, for the enrolled set.
- The number of early withdrawals, reasons for withdrawal and timing of withdrawal will be tabulated by treatment group and overall, for the enrolled set.

## 6.5 Protocol Deviations

All reported protocol deviations will be listed.

QMD Ref: Worldwide-TMP-ST-006-4.0 Effective: 12Aug2019	Governing QMD: Worldwide-SOP-ST-001
Confidentiality Statement	

This document is the property of Worldwide Clinical Trials Inc. and may not be duplicated, copied, altered or removed from company without prior approval from Worldwide Quality Assurance or in compliance with Worldwide Standard Operating Procedures.

Worldwide Clinical Trials Controlled Quality Management Document		
 WORLDWIDE CLINICAL TRIALS	Sponsor:	Global Alliance for TB Drug Development
	Protocol Number:	TBAJ-876-CL001
STATISTICAL ANALYSIS PLAN – PHASE 1		

## 6.6 Baseline Comparability

Comparability of treatment groups with respect to subject demographics and baseline characteristics will be assessed in a descriptive manner, but no formal statistical testing will be performed.

Baseline summaries will be presented by treatment group and overall, for the following variables based on the Safety Analysis Set:

### Demographic Data

- Age at Informed Consent (years)
- Sex
- Ethnicity
- Race, where more than one race is selected the subject will be presented under the ‘Multiple races’ category in the summary but each selected race will be identified in the listing.

### Baseline Characteristics

- Weight at Screening (kg)
- Height at Screening (cm)
- BMI at Screening (kg/m^2)

Contraceptive data collected from female subjects will be listed separately.

## 6.7 Medical History

Prior and ongoing conditions at Screening will be listed for the Safety Analysis Set. Conditions will be coded using the Medical Dictionary of Regulated Activities (MedDRA) version 23.0 primary system organ class (SOC) and preferred term (PT). Any medical condition will be classed as resolved if a stop date is recorded, otherwise, the condition will be classed as ongoing.

## 6.8 Prior and Concomitant Medications

Prior and concomitant medications will be listed for the Safety Analysis Set. Medications will be coded using the World Health Organization (WHO) Drug Dictionary B3 – September 2020 version. Prior medications are defined as all medications starting and stopping before the date of

QMD Ref: Worldwide-TMP-ST-006-4.0 Effective: 12Aug2019	Governing QMD: Worldwide-SOP-ST-001
Confidentiality Statement	

This document is the property of Worldwide Clinical Trials Inc. and may not be duplicated, copied, altered or removed from company without prior approval from Worldwide Quality Assurance or in compliance with Worldwide Standard Operating Procedures.

Worldwide Clinical Trials Controlled Quality Management Document		
 WORLDWIDE CLINICAL TRIALS	Sponsor:	Global Alliance for TB Drug Development
	Protocol Number:	TBAJ-876-CL001
STATISTICAL ANALYSIS PLAN – PHASE 1		

first dose of study drug. Concomitant medications are defined as medications taken on or after the date of first dose of study drug.

## 6.9 Exposure to Study Drug

Extent of exposure (number of doses and duration of exposure [days]) in Part 2 MAD, will be summarized by treatment group for the Safety Analysis Set. All dosing information (Parts 1 and 2, and 3) will be listed.

## 6.10 Statistical Analysis of Pharmacokinetic Data

PK parameters will be calculated as described in section 6.2.12.

PK parameters will be summarized by study part, analyte, cohort (group for Part 3), and/or day for Part 2, using descriptive statistics. PK parameters will also be stratified by gender.

### Dose Proportionality (Parts 1 and 2):

The pharmacokinetic parameters for TBAJ-876, M2, and M3  $C_{max}$ ,  $AUC_{last}$ ,  $AUC_{0-24h}$ ,  $AUC_{0-72h}$  and  $AUC_{inf}$  (Part 1);  $C_{max}$  and  $AUC_{tau}$  (Part 2, Day 1); and  $C_{max}$  and  $AUC_{tau}$ , (Part 2, Day 14) will be compared across doses to assess dose proportionality (i.e., proportionality of a change in systemic exposure with a change in dose). Statistical analyses will be done using a power model (Smith, 2000) of the following general form,

$$\ln(PK) = \ln(\beta_0) + \beta_1 \cdot \ln(\text{Dose}) + \varepsilon,$$

Where

$PK$  is the pharmacokinetic parameter tested (e.g.  $C_{max}$  or  $AUC$ )

$\ln(\beta_0)$  is the y-intercept,

$\beta_1$  is the slope (a value of  $\beta_1 \approx 1$  indicates linearity), and

$\varepsilon$  is an error term

The estimate of  $\beta_1$  with the 90% CIs will be reported along with the associated p-value and the dose range for proportionality. Dose proportionality plots will be created as well.

### Food Effect (Part 1):

Statistical comparison of the PK parameters of TBAJ-876, M2, and M3 exposure ( $C_{max}$ ,  $AUC_{0-24h}$ ,  $AUC_{0-72h}$   $AUC_{last}$ , and  $AUC_{inf}$ ) will be performed using an Analysis of Variance (ANOVA) model for a 2-way crossover design on the ln-transformed data with treatment as the

QMD Ref: Worldwide-TMP-ST-006-4.0 Effective: 12Aug2019	Governing QMD: Worldwide-SOP-ST-001
Confidentiality Statement	

This document is the property of Worldwide Clinical Trials Inc. and may not be duplicated, copied, altered or removed from company without prior approval from Worldwide Quality Assurance or in compliance with Worldwide Standard Operating Procedures.

Worldwide Clinical Trials Controlled Quality Management Document		
 WORLDWIDE CLINICAL TRIALS	Sponsor:	Global Alliance for TB Drug Development
	Protocol Number:	TBAJ-876-CL001
STATISTICAL ANALYSIS PLAN – PHASE 1		

fixed effects and subject as a random effect. Conclusions regarding the results of the statistical analysis of PK parameters across treatments will be based on the ratio of the geometric means expressed as a percent (100×Fed/Fasted) and the 90% confidence interval about the ratio. A lack of food effect will be demonstrated if the 90% confidence intervals are fully contained within the limits of 80.00% to 125.00%.

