		tartrate. The composition of the tablets is as follows: lactose monohydrate, microcrystalline cellulose, povidone, crospovidone, colloidal silicon dioxide, and magnesium stearate. The formulation of the two strengths of tablets is identical and dose proportional.
		Add the following to the end of Container and Closure System:
		TBAJ-876 Tablets 25 mg are packaged as 30-count in 30 cc round high-density polyethylene (HDPE) bottles induction sealed and with 28 mm polypropylene (PP) child resistant closures (CRC). TBAJ-876 Tablets 100 mg are packaged as 30-count in 40 cc round HDPE bottles induction sealed and with 33 mm PP CRC. The tables are stored at 15-30 °C (59-86 °F).

PROTOCOL SYNOPSIS

Name of Sponsor/Company: Global Alliance for TB Drug Development

Name of test product: TBAJ-876

Name of active ingredient: TBAJ-876 Tartrate

Title of study: A Phase 1, Partially Blind, Placebo Controlled, Randomized, Combined Single Ascending Dose with a Food Effect Cohort (Part 1), Multiple Ascending Dose (Part 2), and Relative Bioavailability (Part 3) Study to Evaluate the Safety, Tolerability, Pharmacokinetics of TBAJ-876 in Healthy Adult Subjects

Principal Investigator: [name]

Study Center

Worldwide Clinical Trials Early Phase Services, LLC [name]

Study period:

Part 1: Single ascending dose (SAD) cohorts which includes a Food-effect Cohort: approximately 56 days, from Day -1 to study exit.

Part 2: Multiple ascending dose (MAD) cohorts: approximately 133 days, from Day -1 through completion of clinical procedures on Day 126 followed by a phone call on Day 133.

Part 3: Single dose, open-label parallel relative bioavailability (BA) design: approximately 45 days, from Screening to study exit.

The maximum duration of the study will depend upon the final number and timing of each cohort and the observed terminal half-life $(T_{1/2})$.

Duration of treatment:

Part 1: One single dose of TBAJ-876 Oral Suspension or placebo for TBAJ-876 Oral Suspension

Food-effect Cohort: One single dose of TBAJ-876 Oral Suspension. Subjects will receive TBAJ-876 Oral Suspension in fasted or fed conditions.

Part 2: Multiple doses (14 doses per cohort) of TBAJ-876 Oral Suspension or placebo for TBAJ-876 Oral Suspension

Phase of development: 1

Number of sites enrolling subjects: 1

Part 3: One single dose of 100 mg TBAJ-876 as 1 x 100 mg tablet (either fasted or fed) or 4 x 25 mg tablets (fasted).

Number of subjects (planned):

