9.3 Statistical Analysis

Final statistical analyses will be performed using appropriate software, e.g. PhoenixTM WinNonlin[®] (Version 8.1 or higher, Certara, L.P. in conjunction with the internet-accessible implementation of Pharsight[®] Knowledgebase ServerTM [PKSO; Version 4.0.4 or higher, Certara, L.P.]) and SAS[®] (Version 9.4 or higher, SAS Institute Inc.).

For Parts 1, 2, and 3, PK parameters will be summarized by cohort using descriptive statistics. Summary statistics will also be presented by gender within each cohort.

For Part 1, dose proportionality for exposure parameters (C_{max} , AUCs) will be assessed using a power model approach. Food effect will be assessed using an analysis of variance (ANOVA) with food condition as the fixed effect.

For Part 2, dose proportionality for exposure parameters (C_{max} , AUCs) will be assessed using a power model approach. Steady state for each dose level will be assessed using an appropriate statistical methodology.

For Part 3, Food effect will be assessed using an ANOVA model with food condition as the fixed effect. The relative bioavailability analysis for the two strengths of TBAJ-876 tablets will be assessed using an ANOVA model with the strength of tablet administered under fasting conditions as the fixed effect.

Additional details will be provided in the SAP.

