## 4 SAMPLE SIZE

For Part 1, 7 dose levels are planned. For 7 dose levels, 7 cohorts of 8 subjects will be used, 6 to receive active drug and 2 to receive placebo, all under fasting conditions.

QMD Ref: Worldwide-TMP-ST-006-4.0 Effective: 12Aug2019	Governing QMD: Worldwide-SOP-ST-001
Confidentiality Statement	

This document is the property of Worldwide Clinical Trials Inc. and may not be duplicated, copied, altered or removed from company without prior approval from Worldwide Quality Assurance or in compliance with Worldwide Standard Operating Procedures.

Worldwide Clinical Trials Controlled Quality Management Document		
 WORLDWIDE CLINICAL TRIALS	Sponsor:	Global Alliance for TB Drug Development
	Protocol Number:	TBAJ-876-CL001
STATISTICAL ANALYSIS PLAN – PHASE 1		

The effect of food on bioavailability of TBAJ-876 will be studied in a food-effect cohort comprised of two parallel groups, one fasting and the other fed. The fed group will enroll at least 10 subjects, which will yield complete data for at least 8 subjects if at most 2 fail to complete. For the fasted group, the data from the 6 subjects previously administered 100 mg TBAJ-876 in Cohort 4 (who have already completed the cohort) will be combined with data from 3 additional subjects to be enrolled in this fasted group. This will yield a complete data set for at least 8 subjects if at most 1 fails to complete. Thus, the total number of subjects planned is at least 60 to 70.

For Part 2, 39 subjects are planned to be enrolled. There are 3 cohorts planned. Cohort 1 with 12 subjects per cohort (9 to receive active drug and 3 to receive placebo). Cohort 2 with 13 subjects per cohort (9 to receive active drug and 4 to receive placebo), and Cohort 3 with 14 subjects per cohort (9 to receive active drug and 5 to receive placebo). All doses in Part 2 will be under fed conditions.

For Part 3, 30 subjects are planned to be enrolled. There are 3 groups planned with 10 subjects per group. All subjects will receive active drug under fasted or fed conditions.

Additional cohorts may be enrolled if it is deemed appropriate by the Sponsor to repeat a dose level, to study another dose level, or to increase cohort size (subject numbers).

The number of subjects selected for the study was based on the adequate number considered to provide sufficient safety data. This study has not been formally powered.

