## 5 RANDOMIZATION

In Parts 1 and 2, each subject will receive an assigned treatment (active or placebo) based on the randomization schedule prepared by the unblinded statistician. The unblinded pharmacy staff will ensure compliance with the randomization schedule.

All subjects entering the Part 1 food-effect cohort will receive active drug (TBAJ-876 100 mg). In this food-effect cohort, new subjects will be enrolled in two parallel groups, one fasting (3 additional subjects) and the other fed (10 subjects).

For Part 3, all subjects will be randomly allocated to receive active drug under fasted or fed conditions.

QMD Ref: Worldwide-TMP-ST-006-4.0 Effective: 12Aug2019	Governing QMD: Worldwide-SOP-ST-001
Confidentiality Statement	

This document is the property of Worldwide Clinical Trials Inc. and may not be duplicated, copied, altered or removed from company without prior approval from Worldwide Quality Assurance or in compliance with Worldwide Standard Operating Procedures.

Worldwide Clinical Trials Controlled Quality Management Document		
 WORLDWIDE CLINICAL TRIALS	Sponsor:	Global Alliance for TB Drug Development
	Protocol Number:	TBAJ-876-CL001
STATISTICAL ANALYSIS PLAN – PHASE 1		

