#### Food Effect and Relative Bioavailability (Part 3):

Food effect will be assessed for TBAJ-876, M2, and M3  $C_{max}$  and AUCs using an ANOVA model for parallel study design with food condition as the fixed effect. The relative bioavailability analysis for the two strengths of TBAJ-876 tablets will be assessed for TBAJ-876, M2, and M3  $C_{max}$  and AUCs using an ANOVA model for parallel study design with the strength of tablet administered under fasting conditions as the fixed effect.

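### The SAP plans a 2-way crossover ANOVA with a random subject effect for the Part 1 food effect, but that cohort is two parallel groups with one dose per subject

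*SAP*

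**What the plan says.** SAP 6.10, Food Effect (Part 1), compares Cmax, AUC0-24h, AUC0-72h, AUClast and AUCinf of TBAJ-876, M2 and M3 between fed and fasted. The model is an "Analysis of Variance (ANOVA) model for a 2-way crossover design on the ln-transformed data with treatment as the" "fixed effects and subject as a random effect". No period or sequence term is named. The decision rule follows: "A lack of food effect will be demonstrated if the 90% confidence intervals are fully contained within the" limits 80.00% to 125.00%.

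The design is described differently everywhere else:

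- Protocol Synopsis, Duration of treatment: "Food-effect Cohort: One single dose of TBAJ-876 Oral Suspension. Subjects will receive TBAJ-876 Oral Suspension in fasted or fed conditions".
- SAP 4: the cohort is "comprised of two parallel groups, one fasting and the other fed".
- SAP 5: "new subjects will be enrolled in two parallel groups, one fasting (3 additional subjects) and the other fed (10 subjects").
- Protocol Synopsis (Number of subjects) and SAP 1: the fed subjects are at least 10 and are new; the fasted group is 6 subjects from Cohort 4 plus at least 3 more.

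For the analysis, protocol 9.3 (Part 1) says: "Food effect will be assessed using an analysis of variance (ANOVA) with food condition as the fixed effect". For the tablet food effect in Part 3, the SAP specifies an "ANOVA model for parallel study design with food condition as the fixed effect". SAP 7 states that no changes to the planned analyses were identified.

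**The concern.** A 2-way crossover model needs each subject to be observed under both conditions. Here nobody is. Period would be constant, sequence would be the same variable as food condition, and a subject effect would have one record per level. The model therefore cannot be fitted as described.

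The food effect is a stated secondary objective, and the SAP attaches a pass/fail rule to this interval for 15 comparisons (3 analytes times 5 parameters). If the error term and its degrees of freedom are not defined, two programmers can follow the text and report different limits and, close to 80% or 125%, different verdicts. In addition, the protocol and the SAP name different models for the same analysis, and the difference is not declared.

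**Working it through.** **Inputs.** Fed: at least 10. Fasted: 6 + 3 = 9. Records per subject: 1. Interval: 90%. Limits: 80.00% to 125.00%. The documents give no CV, so it is an assumption throughout.

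**The plan's own figure.** SAP 4 expects complete data for at least 8 per group: 10 - 2 = 8 fed and 9 - 1 = 8 fasted. This reproduces.

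**Can the model be fitted?** With 19 subjects and one record each:

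- Intercept and food condition: rank 2. Adding sequence and period leaves the rank at 2.
- Adding one indicator per subject: rank 19.
- Residual df: 19 - 2 = 17 without subject, 19 - 19 = 0 with subject. At 8 per group: 14 and 0.

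**Are the estimate and its SE affected?** With one record per subject, each observation has variance (subject + residual) = σ², and no two observations are correlated. So SE = σ × √(1/10 + 1/9) = 0.4595σ however σ² is split. On simulated data the contrast, the SE and the REML likelihood were identical at subject shares of 1%, 10%, 50%, 90% and 99%. The ratio and its SE are those of the two-group comparison, and the likelihood cannot separate the two components.

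**What depends on the df?** The log-scale half-width is multiplier × √ln(1 + CV²) × √(1/10 + 1/9). The multiplier is t(0.95, 17) = 1.740. As an illustration of an unstated convention, the large-sample value is 1.645. The ratio 1.6449/1.7396 = 0.9455 means an interval 5.5% narrower on the log scale, with 88.2% coverage instead of 90%.

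At an observed ratio of 1 and an assumed CV of 30%: √ln(1.09) = 0.2936, and 0.2936 × 0.4595 = 0.1349.

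| Multiplier | Half-width | 90% CI | Rule |
|---|---|---|---|
| 1.740 (17 df) | 0.2346 | 79.1-126.4% | not met |
| 1.645 (large sample) | 0.2219 | 80.1-124.8% | met |
| 0 df | none | no interval | undefined |

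**Over what range does the verdict change?** Set the half-width to ln(1.25) = 0.2231 and solve for CV. With 17 df: 0.2231/(1.7396 × 0.4595) = 0.2792, so CV = √(exp(0.2792²) - 1) = 28.5%. With the large-sample multiplier: 0.2231/(1.6449 × 0.4595) = 0.2953, so CV = 30.2%. At a ratio of 1 the two conventions disagree only between these values.

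**At 8 per group.** t(0.95, 14) = 1.761 and √(1/8 + 1/8) = 0.5. The 14-df threshold is 0.2231/(1.7613 × 0.5) = 0.2534, a CV of 25.8%.

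**Context only.** For the parallel analysis with 17 df and a ratio of 1, the 90% CI is 85-117% at a CV of 20%, 82-122% at 25%, 73-136% at 40% and 69-146% at 50%. These widths come from the sample size, not from the wrong model.

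**The case against.** The best defence is that subject is declared random. Food is then a between-subject factor, its error term is subject within food group, and that stratum has 17 df. On this reading the SAP model gives exactly the interval of the proposed correction; 0 df belongs to an empty within-subject stratum, and a programmer who used it would get no interval at all, which is a visible failure. The 1.645 multiplier appears nowhere in the SAP. SAP 9 lists independent programming for the Part 1 food-effect tables, so a divergence should surface before reporting. Protocol 9.3 leaves further detail to the SAP, and the study was not formally powered.

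Much of this limits the size of the problem. The estimate and SE are not biased, the large-sample interval is only an illustration, and the range of CVs where it matters is narrow. The 17-df figure also assumes that all 19 minimum enrollees are analysable; there would be 14 df at 8 per group, and possibly fewer for AUCinf because SAP 6.2.12.4 excludes values with 20% or more extrapolation.

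It does not rescue the text. The 17-df reading is one sensible convention, but the SAP does not state it. Independent programming would reveal a disagreement without saying which interval was pre-specified. Leaving detail to the SAP does not cover naming a design that the study does not have.

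One general-purpose mixed-model routine, fitted to simulated data of this shape, split the variance 50/50 arbitrarily and printed an SE of 0.0437 against 0.0964 from the two-group analysis. That is a numerical artefact of an unidentifiable model, and SAS and WinNonlin were not tested, so it adds nothing to the size given here. It does show that literal execution can be unreliable.

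**Conclusion.** The concern holds and should be fixed. The Part 1 food-effect model in SAP 6.10 does not match the design in the protocol or in the SAP, departs from protocol 9.3 by adding a crossover structure and a subject term, and differs from the SAP's own Part 3 model, while SAP 7 declares no change.

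The food effect remains estimable. What is undefined is the error df, and so the limits of the interval behind the 80.00-125.00% rule. The numerical effect is modest: in the illustration, a 5.5% narrower log-scale interval and a different verdict only for observed CVs of about 28.5% to 30.2%. That range assumes 10 fed and 9 fasted subjects, an observed ratio of 1 and a large-sample multiplier as the alternative convention. The mismatch itself rests on no assumption.

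**What to change.** In SAP 6.10, Food Effect (Part 1), replace the model sentence with: ANOVA for a parallel-group design on ln-transformed data, with food condition as the only fixed effect and no subject effect; geometric mean ratio fed/fasted with its 90% CI from the between-subject residual error, on N - 2 df, where N is the number of subjects analysed for that parameter. This agrees with protocol 9.3 and the Part 3 model, and makes the SAP 7 statement true for this analysis.

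Separately, reconcile two leftover phrases in the protocol with the parallel design: the conditional reference in 3.1 to crossing over one cohort, and the note under Table 11 in 6.7.4 that ties the food-effect sampling windows to each study period. Neither affects the analysis.

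Optionally, state how an interval not contained in the limits will be read. The cost is SAP wording plus the two protocol phrases; no new data are needed.
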